## **17. SUBJECT CONFIDENTIALITY**

At all times throughout this study, all parties shall strictly observe the confidentiality of subject's health information. All data shall be secured against unauthorized access. Each subject participating in this study will have consented to allow access to her data, as described during the informed consent process and documented in the signed informed consent form. Each subject will also sign an Authorization For Release of Protected Health Information (PHI) form granting ContraMed and its designees access to her medical records, should she receive medical care from non-study sites where she gets care (e.g., emergency room, urgent care, etc.). Each subject will be assigned a unique identifier. All eCRFs will be tracked, evaluated, and stored using only this unique identifier. HIPAA guidelines and regulations will be followed.

The Investigator will maintain a confidential study subject list identifying all enrolled subjects. This list will contain the assigned study subject's unique identifier and name. The Investigator bears responsibility for keeping this list confidential. This list will not be provided to the study Sponsor and is only to be used at the study center.

Monitors and auditors will have access to the study subject list and other personally identifying information of study subjects to ensure that data reported in the eCRFs corresponds to the person who signed the consent form and the information contained in the original source documents. Such personal identifying information may include, but not limited to, the subject's name, address, date of birth, gender, race and medical record number.

In an effort to protect subject confidentiality, any source documents copied for monitoring purposes by the Sponsor or designee will be identified using the subject's assigned unique identifier and personal identifying data will be obscured.

## **18. PREGNANCY DETERMINATION AND FOLLOW UP**

Suspected pregnancy will be confirmed with a urine pregnancy test. A positive urine test will be confirmed by a serum test and/or ultrasound as is appropriate. Pregnancies will be promptly confirmed and dated by ultrasound evaluation and medical assessment as needed. Presence or absence of the study device will also be determined by ultrasound. Removal of the study device, if in place, will be performed as deemed appropriate by the study physician and upon obtaining subject consent (note: removal itself may be performed by another clinician, such as a nurse practitioner). Consideration of study device removal should include the following standard of care criteria: If the subject has an intrauterine pregnancy in the first trimester and the study device is seen to be in the uterine cavity or cervix on ultrasound, remove the study device if the retrieval threads are visible. If the retrieval threads are not accessible, the IUD should remain in the uterus until delivery (abortion or term). Subjects will be counseled and followed through completion of pregnancy, and the clinical outcome will be recorded.

## **19. DATA MONITORING AND QUALITY CONTROL**

### **19.1 Monitoring of Clinical Sites and Investigators**

Periodic monitoring visits will be made at the investigational site throughout the clinical study to ensure that the Investigator obligations are fulfilled and all applicable regulations and guidelines are being followed. These visits will ensure that the facilities remain acceptable, the investigational plan is being followed, the IRB and local authorities have been notified of approved investigational plan changes as required, complete records are being maintained, appropriate and timely reports have been made to the Sponsor and/or its designees and the IRB, study device and study device inventory are controlled and the Investigator is carrying out all agreed upon activities. The Sponsor will reserve the right to remove either the Investigator or the investigational site from the study for noncompliance with the investigational plan or regulations. See monitoring plan for full details.

### **19.2 Electronic Case Report Forms (eCRF)**

Electronic case report forms (eCRFs) will be used to collect all subject data during the study

The Investigator is responsible for the accuracy and completeness of all data on the eCRFs.

Sponsor personnel or designee will review completed eCRFs at regular intervals throughout the study. Information on the eCRFs will be compared to information originally recorded on source documents related to the study. Information on the eCRF must match the same information on the source documents or a data query will be issued.

The Sponsor will use the study data for statistical and tracking purposes and will treat the information as confidential.

### **19.3 Data Collection and Management**

Qualified study staff at the investigational site will perform primary data collection. The Sponsor monitors and/or designees will perform clinical study monitoring of 100% of the subjects who pass screening evaluations and undergo LevoCept placement. This monitoring will include review of eCRF data with verification to the source documentation.

All eCRFs will be reviewed for completeness, validity, and consistency. Queries will be generated and resolved with the sites and all protocol deviations will be recorded on the eCRF.

### **19.4 Maintaining Records**

The Sponsor and/or its designees will maintain copies of correspondence, data, shipment of study devices, adverse study device effects and other records related to the clinical study. The Sponsor will maintain records related to the signed Investigator agreements.

### **19.5 Record Retention**

All study records and reports will remain on file for a minimum of two years (or longer if local law or clinic administration requires) after the latter of the following two dates: 2 years after a marketing application is approved, or if an application is not approved, until 2 years after shipment and delivery of the study device for investigational use is discontinued and FDA has been so notified. Study records should only be discarded upon written notification from the Sponsor. All records and reports are subject to inspection at any time.

### **19.6 Investigational Product Accountability**

The Sponsor or designee shall ship investigational study devices only to qualified investigators. The Investigator shall maintain adequate records of the receipt and disposition of all investigational study devices. The Investigator shall return any unused devices, opened or unopened, to the Sponsor or its designees when the study has completed.

### **19.7 Study Closeout**

Upon completion of the clinical study (when all subjects enrolled have completed the last required visit and the eCRFs and queries have been completed), the Sponsor and/or its designees will notify all investigational sites of closeout. Unused study devices, and any unused study materials will be collected and returned to the Sponsor and/or its designees.

### **19.8 Audits and Inspections**

The Investigator will permit access to original medical records and provide all requested information in the event that the Sponsor and/or its designees or national regulatory authorities initiate any audits or inspections. In the case that it is a non-Sponsor initiated audit, the investigator must contact the Sponsor as soon as possible after notification of intent to audit.

### **19.9 Annual, Interim and Final Report**

Annual, interim and final reports will be completed in accordance with the applicable local and federal regulations. A final report will be completed even if the study is prematurely terminated.

## **20. STATISTICAL METHODOLOGY AND ANALYSIS**

A detailed statistical analysis plan will be finalized prior to locking the database to conduct the statistical analysis in accordance with the methods presented below.

### **20.1 Analysis Populations**

The following analysis populations will be created:

All Enrolled: All subjects enrolled into the study.

Intent to Treat (ITT) / Safety: All enrolled subjects who underwent the study device placement procedure, regardless of whether the study device was successfully placed or not.

Evaluable for Pregnancy (EP):

Subjects must meet requirements 1 and 2 to be EP. Subjects must also meet either requirement 3 or requirement 4 to be EP.

1. between 18 to 35 years of age (inclusive) at enrollment
2. at least one report of pregnancy status after being enrolled  
AND
3. have at least 1 cycle of e-diary with intercourse and without any  
backup contraception or emergency contraception (EC)  
OR
4. became pregnant while LevoCept was in place.

Evaluable for Cycle Control (ECYC): all subjects Evaluable for Pregnancy with at least one cycle for which: A) a pregnancy did not occur; and B) there is bleeding related e-diary data.

## **20.2 Disposition of Subjects**

The number of subjects who are enrolled, complete scheduled study visits and who complete the study will be summarized for the All Enrolled population.

## **20.3 Demographic and Other Subject Characteristics**

Subject demographics and pre-treatment characteristics will be summarized for the All Enrolled Population.

## **20.4 Extent of Exposure**

Exposure (number of subjects with LevoCept placed and number of cycles of use) to the study device will be summarized.

## **20.5 Pre-Trial and Concomitant Medications**

Concomitant medications include any medication or health product (any prescription medications or over-the-counter preparations) taken during the study. Pre-trial medications include any contraception or medication used to treat a prior cervical infection taken within 30 days of screening. The number and percentage of subjects using medications, as captured on the Concomitant Medication eCRF, will be tabulated according to the medication's World Health Organization Anatomical Therapeutic Drug Class and Generic Term. Pre-trial and concomitant medications will be presented separately.

## **20.6 Primary Outcome**

The primary outcome measure is effectiveness and will be evaluated as absence of pregnancy during LevoCept use. Pregnancies judged to have occurred while a study device was in place (determined by ultrasound and medical assessments) will be included in the analysis of pregnancies.

For the primary evaluation of effectiveness, the Pearl index (and 95% confidence intervals) will be calculated in subjects aged 18-35 at the time of LevoCept placement through the date of LevoCept removal or pregnancy, excluding the following (unless the subject became pregnant in the cycle):

- Cycles where back-up contraception use was reported by the patient
- Cycles with no intercourse.
- Cycles in which emergency contraception was used

The Pearl Index is based on 28-day cycles and defined as the number of pregnancies per 100 woman-years (with one year comprising 13 28-day cycles). The cycle is defined as 28 days with the day of LevoCept placement as cycle 1

day 1. Pearl index will be summarized annually for each of the 3 years and cumulatively.

The EP population will be used for the primary evaluation of effectiveness.

Life table (Kaplan-Meier method) analyses will be used as further assessment of pregnancies. Pregnancy rate will also be summarized annually for each of the 3 years and cumulatively.

## **20.7 Safety and Other Outcome Measures**

All safety and other outcome measures will be analyzed using the ITT/Safety Population unless noted otherwise. Confidence intervals will be provided to support interpretation of the observed safety rates.

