6.1 General Methodology

Analyses will be implemented using SAS® 9.4 or above. In general, all efficacy and safety variables will be summarised using descriptive statistics and graphs as appropriate. Continuous variables will be summarised by descriptive statistics (sample size (n), mean, standard deviation (SD), minimum, median, and maximum). Categorical variables will be summarised in frequency tables (frequencies and percentages). Time to event variables will be summarised by Kaplan-Meier estimates of median and quartile time to events. Individual data will be presented in subject listings.

Means and medians will be displayed with one more decimal place than the collected data, and SDs will have one more decimal place than the means and medians. Minimum and maximum will be displayed with the same number of decimal places as the collected data. Percentages will be rounded to one decimal place.

No formal statistical testing will be performed on subject disposition, demographic, baseline characteristic, and safety data. Where appropriate, point estimates, together with their 95% confidence intervals will be presented.

Only observed data, with no data imputation, will be used for the efficacy analyses unless otherwise specified. Safety analyses will also be conducted on the observed data. However, for the start date/time of an AE or medication being partially or completely missing, the worst case scenario will be applied. That is, the AE will be assumed to be treatment emergent, and the medication will be considered to be concomitant.

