6.2.9 Safety Variables

All safety analyses will be based on safety analysis population unless otherwise specified. Descriptive statistics will be used to summarise the safety outcomes. No inferential analyses of safety data are planned.

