6.2.9.1 Adverse Events

Number of AEs will be summarised by SOC and/or PT for the following categories of TEAEs: all AEs, SAEs, AEs related to study device, AEs related to study device placement/removal procedure, AEs leading to death, AEs leading to study device removal and AEs as primary reason for exiting study. Patients with more than one occurrence of the same SOC (PT) will be counted only once within the SOC (PT) categorisation.

AEs will also be summarised similarly by severity (i.e. mild, moderate, severe), relationship to study device (i.e. not related, unlikely related, probably related, related), relationship to placement/removal procedure (i.e. not related, unlikely related, probably related, related) and onset time frame (i.e. 0-3 months, >3-6 months, >6-12 months, >12 months). Should a subject experience more than one occurrence of the same SOC (PT), the subject's worst occurrence (worst intensity/most related causality) will be retained in the tabulation.

All AEs, including AEs that started prior to the study device placement, will be presented in data listings. In addition, separate listings of all SAEs, AEs related to study device, AEs related to study device placement/removal procedure, AEs leading to death, AEs leading to study device removal and AEs as primary reason for exiting study will be provided. In case of any AEs reported from study device insertion failure subjects, selected AE tables will be repeated for all enrolled subjects for all AEs.

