10.2 Population Summary Conventions

- Population(s) represented on the tables or data listings will be clearly identified in the last title of the Table as "Population: <name of population>" and will be identical in name to that identified in the protocol or SAP.
- Population sizes may be presented in the column header as (N=xxxx), where appropriate.
- Population sizes shown with summary statistics are the samples sizes (n) of subjects with non-missing values.
- All population summaries for categorical variables will include all categories that were planned and for which the subjects may have had a response. Percentages corresponding to null categories (cells) will be suppressed.
- All population summaries for continuous variables will include: N, mean, median, SD, minimum, maximum and n. Other summaries (e.g., number missing, quartiles, 95% intervals) may be used as appropriate.
- All percentages are rounded and reported to a single decimal point (xx.x). A percentage of 100% will be reported as (100). No value of 0% will be reported. Any computation of percent that results in 0% is to be presented as a blank.

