Some Pain	n (%)
Painful	n (%)
Moderately Painful	n (%)
Very Painful	n (%)
Medication given during the procedure	
n	n
Yes	n (%)
No	n (%)
Mechanical Dilatation	
n	n
Yes	n (%)
No	n (%)

Note: Percentages are based on the number of subjects specified in the column header, i.e. N, unless small n is specified for each category.

Reference: Listing xxx.

Program Location: \\xx\xxx\xxx\xxx\xxxxxx\xxxxxxxxxxxxxxxx\xxxx\xxxxx.sas

date

time

CONFIDENTIAL

Sebela Pharmaceuticals Development LLC
CMDOC-0022

Page x of y

Table 14.3.5.3
Device Expulsion/Removal and Subject Pain During the Procedure (Safety Population)

Description	All Subjects (N=xx) n (%)
Cumulative 1-Year Device Expulsion Rate	n (%)
Cumulative 1-Year Device Removal Rate	n (%)
Cumulative 2-Year Device Expulsion Rate	n (%)
Cumulative 2-Year Device Removal Rate	n (%)
Cumulative 3-Year Device Expulsion Rate	n (%)
Cumulative 3-Year Device Removal Rate	n (%)
Device Expel Prior to This Visit	
n	n
Yes	n (%)
No	n (%)
If Yes, Expulsion Status	
n	n
Complete	n (%)
Partial	n (%)
Was removal accomplished by pulling the strings Without Difficulty	
n	n
Yes	n (%)
No	n (%)
If No, Select All That Apply:	
n	n (%)
Required significant force to pull out with strings	n (%)
Required use of ultrasound guidance	n (%)
Required use of Alligator forceps	n (%)
Required use of IUD hook	n (%)
Required use of other instrument	n (%)
Unable to remove in office initially, required second office visit for successful removal	n (%)
Unable to remove in office - removed in OR	n (%)
Other	n (%)

Note: Percentages are based on the number of subjects specified in the column header, i.e. N, unless small n is specified for each category.
Reference: Listing xxx.

Program Location: \\xx\xxx\xxx\xxxxxx\xxxxxxxxxxxxxxxx\xxxx\xxxxx.sas

date

time

CONFIDENTIAL

Sebela Pharmaceuticals Development LLC
CMDOC-0022

Page x of y

Table 14.3.5.3
Device Expulsion/Removal and Subject Pain During the Procedure (Safety Population)

Programmers note: Continued table

Description	All Subjects (N=xx) n (%)
Ease of Device Removal	
n	n
Very Easy	n (%)
Easy	n (%)
Neither Easy nor Difficult	n (%)
Difficult	n (%)
Very Difficult	n (%)
Device Removal Pain	
n	n
No Pain	n (%)
Some Pain	n (%)
Painful	n (%)
Moderately Painful	n (%)
Very Painful	n (%)
Medication Given During the Procedure	
n	n
Yes	n (%)
No	n (%)

Note: Percentages are based on the number of subjects specified in the column header, i.e. N, unless small n is specified for each category.

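### The protocol promises confidence intervals for safety rates; the SAP leaves them to a discretionary clause, assigns them to no safety table, and does not record the departure

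*Protocol*

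**What the plan says.** Protocol 20.7 states, for safety and other outcomes: "Confidence intervals will be provided to support interpretation of the observed safety rates". It gives no confidence level, method or list of rates. Protocol 20 says a detailed SAP will be finalised "to conduct the statistical analysis in accordance with the methods presented below".

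The SAP treats the matter in four places:

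- SAP 6.1 rules out formal testing of several kinds of data, safety included. Its next sentence reads: "Where appropriate, point estimates, together with their 95% confidence intervals will be presented".
- SAP 6.2.9, the safety section, reads: "Descriptive statistics will be used to summarise the safety outcomes. No inferential analyses of safety data are planned".
- SAP 6.2.9.1 ("Number of AEs will be summarised by SOC and/or PT for the following categories of TEAEs") and SAP 6.2.9.7 (expulsion and removal) name no interval.
- SAP 10.2 says "Other summaries (e.g., number missing, quartiles, 95% intervals) may be used as appropriate", but this stands in the bullet on continuous variables, not event percentages.

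The adverse event, serious adverse event, expulsion and removal shells show n and n (%) only. Table 14.3.5.3, for example, has a row "Cumulative 1-Year Device Expulsion Rate" with n (%). The only table shell with an interval column is Table 14.2.1, the Pearl Index. SAP 8.2 lists two changes from the protocol, to the safety population and to the evaluable-for-pregnancy population. Neither concerns intervals.

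**The concern.** A firm protocol commitment becomes an optional one in the SAP, the section specific to safety points away from it, and no output implements it. Nothing records that this was intended.

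The stated purpose of the study is to supply safety and effectiveness data to support starting a Phase III study. With at most about 250 women, events such as perforation, ectopic pregnancy or pelvic infection are likely to appear as counts of zero, one or two. The percentage alone then says little, and the upper limit is the useful quantity. SAP 7 applies the same analyses to the one-year interim report, so both reports would share the gap.

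**Working it through.** The documents give no safety rate, safety interval or safety precision target, so there is no figure of theirs to reproduce. The check has three parts.

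**1. Commitment against implementation**

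| Place | Content | Interval for a safety rate? |
|---|---|---|
| Protocol 20.7 | Intervals will be provided | Yes, unconditional |
| SAP 6.1 | Intervals where appropriate | Possible, unassigned |
| SAP 6.2.9 | Descriptive; nothing inferential | None named |
| SAP 6.2.9.1, 6.2.9.7 | Counts and rates | None named |
| Safety shells (14.3.1.x, 14.3.5.3) | n, n (%) | None |
| SAP 8.2 | Two population changes | Not mentioned |

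**2. Size of what is missing**

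Inputs: N = 250 is the planned maximum (Protocol, Investigational Plan Summary). The SAP Safety population counts only successful placements and its size is not given, so 240 and 225 are added as assumed values.

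Exact (Clopper-Pearson) two-sided 95% limits for x events in N are the 0.025 quantile of Beta(x, N − x + 1) and the 0.975 quantile of Beta(x + 1, N − x). For x = 0 the lower limit is 0 and the upper limit is 1 − 0.025^(1/N). At N = 250 this is 1 − 0.025^(1/250) = 1.46%.

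| Events | N = 250: rate (95% limits) | N = 240: upper limit | N = 225: upper limit |
|---|---|---|---|
| 0 | 0% (0 to 1.46%) | 1.53% | 1.63% |
| 1 | 0.40% (0.01 to 2.21%) | 2.30% | 2.45% |
| 2 | 0.80% (0.10 to 2.86%) | 2.98% | 3.17% |
| 5 | 2.00% (0.65 to 4.61%) | 4.79% | 5.11% |

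The chance of seeing no case among 250 women is (1 − p)^250, which is 8.1% at a true risk p of 1%, 28.6% at 0.5% and 77.9% at 0.1%. An observed zero is therefore weak evidence against a risk of one in 200.

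**3. Would a column of binomial intervals in the existing shells be enough?**

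- *Zero counts.* Tables by preferred term are built from reported terms, so an event that never occurred has no row. SAP 10.2 also prints 0% as a blank. Protocol 20.7 lists events deserving special attention, but the SAP's table index has no table for them.
- *Denominators.* SAP 5.3 restricts Safety to successful placements, so an event during a failed insertion falls outside it. SAP 6.2.9.1 provides for this with selected All Enrolled tables. The removal and expulsion rates in SAP 4.2 are defined over enrolled subjects, while Table 14.3.5.3 uses the Safety population.
- *Cumulative rates.* Continuation after 12 months is optional, so women leave observation at different times. A binomial interval on a 2- or 3-year proportion treats everyone as fully followed. SAP 4.2 also counts any removal, and SAP 6.2.9.7 runs year 3 from day 729 onward, so planned end-of-study removals are included. The protocol's measure was safety-related removal.

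**The case against.** A reader might infer that the SAP plans no safety intervals at all, or forbids them. The documents do not support that. SAP 6.1 drops tests but keeps 95% intervals where appropriate, immediately after a sentence that names safety data. The statement in SAP 6.2.9 can be read as excluding hypothesis tests only. On that reading it is arguable whether there is a change for SAP 8.2 to list. Protocol 20.7 names no particular rates, so it does not promise an interval for every output.

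The harm is also limited. Where n and N are printed, anyone can compute an exact limit for a simple proportion. No safety decision rule in either document depends on an interval: monitoring is by the Medical Monitor, with a committee if more than one pregnancy is reported. The data collected and the point estimates are unaffected.

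Most of this stands, and it keeps the point to a correction of specification. It does not remove it. The clause in SAP 6.1 names no rate, method, denominator or table, and the more specific section and every safety shell lead the other way. Recovery from n and N also fails where an event has no row, and it does not give a valid interval for a cumulative rate with unequal follow-up.

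**Conclusion.** The point holds as a mismatch between protocol and SAP. An unconditional commitment is left to discretion, assigned to no safety output, and not recorded as a change. It does not hold as a claim that intervals are ruled out, or that the safety data would be uninterpretable.

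The size is modest. At N = 250, zero events is compatible with a risk of up to about 1.5%, and one event with 0.01% to 2.2%. At an assumed N = 225 the zero-event limit is about 1.6%. These figures are illustrative: they assume a simple proportion with every woman counted in the denominator, and the actual Safety N is not stated. The correction is worth making before the tables are produced, but nothing in the study's conduct depends on it.

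**What to change.** - **Wording.** Change SAP 6.2.9 to say that no hypothesis tests will be done and that 95% confidence intervals will be presented for listed safety rates. This agrees with SAP 6.1 and Protocol 20.7. If the sponsor prefers no intervals, record and justify that in SAP 8.2.
- **Adverse event rates.** Specify exact (Clopper-Pearson) 95% intervals for any serious adverse event, any device-related or procedure-related adverse event, and any adverse event leading to device removal. Tables 14.3.1.1.1 and 14.3.1.1.2 already have these rows and need one column.
- **Intrauterine-device events.** Add one short table with fixed rows for the events listed in Protocol 20.7, such as perforation, ectopic pregnancy and pelvic infection. Print zero counts with their upper limit, as an exception to the blank-for-zero rule in SAP 10.2.
- **Denominators.** State one for each rate. Use All Enrolled for placement-related events, because SAP Safety excludes failed placements.
- **Expulsion and removal.** Report cumulative expulsion and safety-related removal as Kaplan-Meier estimates with 95% intervals, not binomial ones. SAP 6.1 already names Kaplan-Meier for time-to-event variables. Define safety-related removal and state how planned removals and other exits are censored.

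The cost is one extra column, one short table and the choice of rates and denominators. No new data are needed. Limiting the list avoids placing an interval on every preferred term.
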